5.1 Primary objective

To determine whether, in patients hospitalised for COPD exacerbations and receiving conventional treatment, the addition of metformin, as compared with placebo, ameliorates hyperglycaemia.

5.2 Secondary objectives

To determine whether, in patients hospitalised for COPD exacerbations and receiving conventional treatment, the addition of metformin, as compared with placebo, produces effects on clinical outcome, and measures of inflammation, steroid sensitivity, and airflow obstruction, which merit further study.

The data collected in relation to the secondary objectives will be hypothesis-generating. They will also be used to inform the selection of appropriate end points, and as a basis for sample size calculations, for a future larger study.

6 Trial design

6.1 Overall design

This is a randomised, double-blind, parallel-group, placebo-controlled trial. An overview of the study is provided in the accompanying schematic diagram.

A double-blinded design has been adopted to provide the best possible evidence for the efficacy of metformin in this context by minimising the risk of bias. Blinding will be implemented by means of visually identical active and placebo treatments.

6.2 Study population

The sample size was originally set at 46 patients, randomised equally to metformin or placebo. From Substantial Amendment 4 approval, this is increased to 69 patients, randomised to metformin or placebo in a 2:1 ratio. The patients will be drawn from the population of patients admitted to the study sites with an exacerbation of COPD, and who are able to enter the study within 48 hours of admission.

6.3 Dosage regimen and rationale

The dose range for metformin hydrochloride is 500–2550 mg/day. However, the maximal anti-hyperglycaemic effect is achieved at 2000 mg/day⁴⁶ and this is the usual maximal dose.³⁹ To minimise the risk that a negative result arises as a consequence of an insufficient dose, we have selected a dose of 2000 mg/day.

It is recommended that metformin should be given in divided doses with or after meals.³⁶ Metformin 2000 mg/day can be conveniently administered as two 500 mg tablets taken twice daily. Ideally, doses should be equally separated, but for practical purposes we will recommend that they be taken at least 8 hours apart, with or up to 20 minutes after breakfast and evening meals. This recommendation is broadly consistent with that used in a large randomised controlled trial.⁶⁹

6.4 Treatment period

[figure not shown]
The duration of hospitalisation for COPD exacerbations is variable. In a study conducted in this hospital,¹⁴ the median length of stay was 9 days (interquartile range, 5–17 days). In a more recent audit and service evaluation study in this hospital, of patients with diabetes and COPD exacerbations, the median length of stay was 8 days (interquartile range, 4–16 days; range 0–75 days). To avoid the introduction of bias (whereby, for example, individuals who were less unwell and thus had a shorter stay would have a lower exposure to the study drug), we have elected to adopt a standardised treatment period for all participants. A period of 28–35 days was selected, to capture the full duration of hospitalisation for the considerable majority of patients, and most of the recovery period. In a prospective study of 91 patients, who experienced 504 exacerbations, the total symptoms score had recovered by day 35 in 86.1% of exacerbations. A 7-day period of leeway was selected to take account of potential difficulties arranging a follow-up appointment (due to weekends, public holidays, and patient/staff availability), while ensuring that the study drug can be continued until the date of that appointment. Follow-up appointments will take place at the site of recruitment.

6.5 Concomitant treatment

All participants will receive systemic corticosteroids (prednisolone 30 mg daily) for a minimum of 7 days. Otherwise, all care for the COPD exacerbation and co-morbidities will be at the discretion of the treating physicians. Tapering and cessation of steroid therapy and any use of antibiotics will also be at the discretion of the treating physician.

The use of other oral anti-hyperglycaemic medications will not be permitted. However, the use of insulin will be permitted during the inpatient phase for the treatment of hyperglycaemia that is significantly and persistent above 7.8 mmol/L (pre-meal readings) and/or 10 mmol/L (random readings), in line with current guidelines.³³ The decision to administer insulin under these circumstances, and the choice formulation and dose, will be at the discretion of the treating physician.

6.6 Schematic of trial design

7 Inclusion and exclusion criteria

7.1 Inclusion criteria

(1) Diagnosis of COPD based on at least one of the following criteria:

- Previously recorded airflow obstruction on spirometry (FEV1 <80% predicted, FEV1:FVC <70% predicted), without evidence of complete reversibility
- Previous diagnosis of COPD by a respiratory physician
- Exertional breathlessness, chronic cough, or regular sputum production, in a patient who has ≥10 pack-years smoking history

(2) Hospitalisation for exacerbation of COPD, defined by the presence of at least two of the following major features, or one major symptom and one minor feature.

Major features:

- Increased breathlessness
- Increased sputum volume
- Increased sputum purulence

Minor features:

- upper respiratory infection within the past 5 days
- fever without other cause
- increased wheezing or cough
- increase in respiratory rate or heart rate by 20% as compared with baseline

(3) Age ≥35 years

(4) Expected to remain in hospital for ≥48 hours.

7.2 Exclusion criteria

Any one of the following features

Criterion	Definition
Prior diagnosis of diabetes mellitus requiring insulin or oral hypoglycaemic therapy	Patient-reported diagnosis of diabetes, or a documented record of diabetes mellitus in the available clinical notes, requiring insulin or oral hypoglycaemic treatment
Hypersensitivity to metformin hydrochloride or to any of the excipients	Patient-reported prior reaction, or documented in available case notes
Renal impairment	Estimated glomerular filtration rate (eGFR) <45 mL/minute/1.73 m ² (using the modification of diet in renal disease (MDRD) four-variable equation), serum creatinine concentration >130 µmol/L, or a requirement for renal-replacement therapy

Severe sepsis	
Sepsis with at least one feature of organ dysfunction or tissue hypoperfusion.
 
Sepsis is defined as suspected or proven infection, plus at least two of the following features (unless they are normal for that patient at baseline):
 
 • temperature >38.3 or <36°C • white cell count <4 or >12 × 10⁹/L • acutely altered mental status • blood glucose >8.3 mmol/L 
Severe sepsis is defined as sepsis in conjunction with at least one feature of organ dysfunction or tissue hypoperfusion:
 
 • renal: creatinine >177 µmol/l or UO <0.5 ml/kg/hr for 2 hrs • hepatic: bilirubin >34 µmol/L • coagulation: platelets <100 × 10⁹/L, INR>1.5 or APTT >60 seconds • tissue hypoperfusion: any one of, systolic blood pressure systolic <90 mmHg, mean blood pressure <65 mmHg, a reduction of >40 mmHg from the patient's normal systolic blood pressure, or lactate >2 mmol/L.
Metabolic acidosis	Arterial or venous blood pH below the lower limit of normal and an arterial or venous bicarbonate concentration (measured or calculated) below the lower limit of normal
Decompensated type 2 respiratory failure	Partial pressure of carbon dioxide in arterial blood higher than the upper limit of normal, with arterial blood pH below lower limit of normal
Severe congestive cardiac failure	Clinical diagnosis of congestive cardiac failure by the treating physicians on the basis of typical symptoms and/or signs and/or results of investigations, which is felt to be the cause of shortness of breath at rest
Acute coronary syndrome	Clinical diagnosis of acute coronary syndrome by the treating physicians on the basis of typical symptoms and/or signs and/or results of investigations, and for which the patient is receiving treatment (likely to include aspirin, clopidogrel and low molecular weight heparin or fondaparinux, depending on local policy) at the time of screening
Hepatic insufficiency	Previous clinical, radiographic or histological diagnosis of liver cirrhosis, as reported by the patient or recorded in their hospital case notes; or a clinical suspicion of liver disease in conjunction with a serum bilirubin concentration >34 µmol/L
Excessive alcohol consumption	Patient-reported regular alcohol consumption of ≥56 units per week for men or ≥42 units per week for women, representing more than twice the UK recommended upper limits for sensible drinking
Malnourished or at high risk for malnutrition	Malnutrition Universal Screening Tool (MUST) ⁷⁰ score ≥2
Moribund or not for active treatment	Treating clinician and/or investigator judgement that the patient is unlikely to survive to hospital discharge, and/or the resulting discontinuation of treatments for the underlying condition
Admitted to critical care unit	Current admission of the patient to the any intensive care or high dependency unit, or a plan to do so imminently
Unable to give informed consent	
An investigator or physician judgement that the patient lacks the capacity to reach an informed decision on the appropriateness of their participation in the trial, due to an inability to:
 
 • understand the information relevant to the decision • retain that information • use or weigh that information as part of the process of making the decision, or • communicate that decision
Pregnancy or lactation	Patient-reported pregnancy or lactation, and/or a positive result from a urinary pregnancy test

8 Recruitment

Patient recruitment at a site will only commence once the trial team has ensured that the following approval/documents are in place:

- The REC and regulatory (MHRA) approvals
- A signed Clinical Trial Site Agreement (CTSA)
- Final sponsorship and host site approval
- The site/trial initiation visit has taken place

8.1 Subject recruitment process

Potential participants will be identified by doctors in the clinical care team, who are also part of the study team. Potentially eligible participants will be identified as those likely to meet the inclusion criteria. Potential participants shall be approached by a doctor from the clinical care and study teams, and informed them that a research project is underway, which they may be eligible to take part in should they wish. If the patient requests further information, the doctor will provide an overview of the project, including its purpose, nature, burdens, and risks; and will emphasise that participation is entirely voluntary. If the patient expresses interest in participating in the trial, the doctor will provide them with a copy of the patient information leaflet and explain its contents. If the patient remains positive about potential participation, informed consent will then be sought.

9 Study procedures and schedule of assessments

9.1 Informed consent

Informed consent will be obtained by the Principal Investigator, Chief Investigator, or a nominated deputy as recorded on the delegation log. Only those members of the study team who have clinical responsibility for the care of patients under the care of the general medical service will be permitted to undertake informed consent. All individuals taking informed consent will have received training in Good Clinical Practice and the study protocol, and have been delegated this duty by the CI/PI on the delegation log.

Consent to enter this study will be obtained after a full account has been provided of its nature, purpose, risks, burdens and potential benefits, and the patient has had the opportunity to deliberate. The patient will be allowed to specify the time they wish to spend deliberating, usually up to 24 hours. Periods shorter than 24 hours will be permitted if the patient feels that further deliberation will not lead to a change in their decision, and provided the person seeking consent is satisfied that the patient has deliberated sufficiently on the information given. This provision has been made with the support of our Patient Advisory Group. Likewise, periods longer than 24 hours will be permitted should the patient request this and while they remain potentially eligible for study entry.

The Investigator or designee will explain that the patients are under no obligation to enter the trial and that they can withdraw at any time during the trial, without having to give a reason.

A copy of the signed Informed Consent will be given to the participant. The original signed form will be retained at the study site.

If new safety information results in significant changes in the risk–benefit assessment, the patient information leaflet (PIL) will be reviewed and updated if necessary. All subjects, including those already being treated, will be informed of the new information, given a copy of the revised PIL and their consent to continue in the study will be sought.

9.2 Randomisation procedure

Prior to Substantial Amendment 4 approval, patients were allocated to metformin or matched placebo by equal group random allocation in blocks of four at Chelsea and Westminster Hospital and blocks of six at St George's Hospital and other sites. Following Substantial Amendment 4 approval, patients will be allocated in a 2:1 ratio to metformin or placebo in blocks of six, with a corresponding increase in the sample size. This amendment was made to increase the number of patients exposed to active drug, so that more robust conclusions can be drawn with respect to the feasibility, safety and tolerability of this agent in the trial population.

Randomisation lists will be produced in advance by the drug manufacturer (Bilcare [GCS] Europe Ltd), and will be provided to the Pharmacy department for the purposes of allocation and/or emergency unblinding. An SOP on the blinding and unblinding procedure will be prepared prior

to study commencement. Randomisation will be performed by the IMP manufacturer in accordance with the method agreed by the study team and trial statistician.

Following allocation to a study treatment, patients will be given a trial participant card, which will have the study title, IMP details, patient trial number and contact details for advice and emergency unblinding.

9.3 Emergency unblinding

The blinded treatment allocation will be held within the Pharmacy Site File. Access to the randomisation code for a participant before the completion of the trial will be permitted in exceptional circumstances if it is necessary to determine subsequent best care for the participant, or for another person suspected to have ingested the study treatment of a known trial participant.

In the event of an emergency and/or clinical requirement for the blinded study treatment allocation to be revealed, the enquirer will contact the relevant Pharmacy Department as described on the participant study card. This service is available 24 hours per day. During working hours, the enquirer should contact the Pharmacy Clinical Trials team. Outside of office hours, the enquirer should request that switchboard bleep the on-call pharmacist. The Pharmacy Clinical Trials team procedures require that the Chief Investigator or Principal Investigator is contacted to obtain permission before treatment allocation is revealed to the enquirer.

9.4 Screening assessments

Patients' eligibility for inclusion shall be screened by reviewing the clinical history, concomitant medications, and examination, which all have already been obtained as part of routine care. Any components of the history or examination that are required to determine eligibility but have not been documented as part of routine care will be obtained during this visit.

9.5 Treatment procedure

Dosing schedule (treatment and placebo arms):

- Day 1: one capsule taken after food following first mealtime after randomisation
- Day 2: one capsule taken after breakfast time and one capsule after evening mealtime
- Day 3: two capsules taken after breakfast time and one capsule after evening mealtime
- Day 4 until follow-up (day 28–35): two capsules taken after breakfast time and two capsules after evening mealtime

9.6 Summary flow chart of study assessments

Day	IMP administration	Assessments
1	One capsule	Capillary glucose concentration (thereafter repeated before and 2 hours after each mealtime, and at approximately 22:00) COPD Assessment Test (CAT) Exacerbations of Chronic Pulmonary Disease Tool (EXACT) Malnutrition Universal Screening Tool (MUST) Renal profile, liver profile, CRP, lactate, random glucose, HbA1c Serum sample saved
2	One capsule twice daily	Exacerbations of Chronic Pulmonary Disease Tool (EXACT) Capillary glucose (as above) CRP Food chart if admission MUST score 1 (medium risk)
3	Two capsules morning, one capsule evening	Exacerbations of Chronic Pulmonary Disease Tool (EXACT) Capillary glucose (as above) CRP measured daily to day 7 Food chart if admission MUST score 1 (medium risk)
Day 4 until discharge	Two capsules twice daily	Exacerbations of Chronic Pulmonary Disease Tool (EXACT) Capillary glucose (as above) CRP measured daily to day 7 Safety parameters (renal function, liver enzymes, plasma lactate, venous glucose) measured at least every 72 hours until day 7 (more often if deemed necessary by study team or clinical team), then at a frequency appropriate for the clinical condition of the patient (no less often than once-weekly)
Day of discharge	Two capsules twice daily	Capillary glucose (as above, until time of discharge) Exacerbations of Chronic Pulmonary Disease Tool (EXACT) COPD Assessment Test Spirometry CRP Serum sample saved
Day of discharge until follow-up	Two capsules twice daily	Exacerbations of Chronic Pulmonary Disease Tool (EXACT)
Follow-up (day 28–35)	Two capsules in the morning	Structured interview and pill count COPD Assessment Test (CAT) Weight, height and waist circumference Spirometry Venous glucose, HbA1c, lactate, CRP Serum sample saved
12 weeks	None	Vital status (electronic patient record) Hospital admissions (self-reported and electronic patient record) COPD Assessment Test (returned by post) Antibiotic and steroid courses (self-reported) Diagnosis and/or treatment for diabetes (self-reported)

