In this study, we consider there to be a risk of lactic acidosis related to the underlying condition (COPD) and commonly associated comorbidities (such as respiratory failure, heart failure, renal failure and severe sepsis). As noted above, the lactate levels and prognosis observed in cases of lactic acidosis are believed to be dictated by with the severity of the underlying condition, rather than to the presence or plasma concentration of metformin.^{40,68} Nevertheless, given the lack of certainty over the safety of metformin therapy in such settings, and to avoid potential confusion over the aetiological agent, we shall stop or suspend the study drug if a condition develops in which there is a high risk of lactic acidosis, or if the plasma lactate concentration rises above pre-specified levels.

Further, we consider that there is a small but genuine risk of metformin-associated lactic acidosis if metformin is allowed to accumulate due to renal failure. To mitigate this, we will monitor the renal function regularly while the participant is an inpatient (when, due to the severity of their concurrent illnesses, the risk of developing renal failure is greatest), and stop or suspend the study treatment if the estimated GFR falls, or the serum creatinine rises, above pre-specified levels.

We judge that the risk of metformin-associated lactic acidosis outside the situations described above is extremely low. This risk must be balanced against the seriousness of the condition under study. As noted above, the 90-day mortality rate following hospitalisation for a COPD exacerbation is 13.9%; the 5-year mortality rate exceeds 50%. Observational data suggest that

lowering blood glucose concentration may offer the prospect of substantial benefit. As such, our assessment is that the risk–benefit balance lies in favour of undertaking this trial.

5 Study objectives

The overarching research question for this body of work is to ascertain whether metformin improves recovery from COPD exacerbations. This pilot study will address two more limited questions, as a basis for future trial design.

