Decompensated hypercapnic respiratory failure	Partial pressure of carbon dioxide in arterial blood higher than the upper limit of normal, with arterial blood pH below lower limit of normal	Resolution of acidosis and no requirement for assisted ventilation for at least 48 hours.
Severe sepsis	As defined in section 7.2 (exclusion criteria)	Resolution of the episode of severe sepsis, and clinical stability for at least 48 hours, as determined by the study investigators, with input from the treating physicians as necessary
Metabolic acidosis	An arterial or venous blood pH below the lower limit of normal and an arterial or venous bicarbonate concentration (measured or calculated) below the lower limit of normal.	Resolution of the metabolic acidosis, and clinical stability for at least 48 hours, as determined by the study investigators, with input from the treating physicians as necessary (provided the criteria for discontinuation due lactate accumulation or acidosis are not met, see below)
Renal impairment	Estimated glomerular filtration rate (eGFR) <45 mL/minute/1.73 m ² or serum creatinine >130 µmol/L	Estimated GFR ≥45 mL/minute/1.73 m ² or serum creatinine ≤130 µmol/L, and it is judged that the cause of the deterioration has resolved and is unlikely to recur
Hepatic insufficiency	A clinical suspicion of liver disease in conjunction with a serum bilirubin concentration >34 µmol/L	None
Alcohol withdrawal syndrome	Clinical diagnosis of alcohol withdrawal syndrome	None
Acute coronary syndrome	Diagnosis of acute coronary syndrome by the treating physicians and/or the initiation of treatment with aspirin, clopidogrel and heparin (low molecular weight or unfractionated, at a dose recommended for the treatment of acute coronary syndrome)	The diagnosis is refuted (for example, on the basis of serial cardiac troponin measurements, or following review by a cardiology specialist)
Severe cardiac failure	Clinical diagnosis of cardiac failure by the treating physicians and/or investigator on the basis of typical symptoms and/or signs and/or results of investigations, which is leading to shortness of breath at rest	None

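### A patient discharged by Day 3 goes on to 2000 mg/day at home with no scheduled creatinine after Day 1 and no scheduled lactate until the day 28–35 visit

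*Protocol*

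**What the plan says.** **Schedule (Protocol 9.6).** Day 1 includes renal profile and lactate. The Day 2 and Day 3 rows list symptom scores, capillary glucose, CRP and, where relevant, a food chart. The safety panel returns in the row that runs from Day 4 to discharge: "Safety parameters (renal function, liver enzymes, plasma lactate, venous glucose) measured at least every 72 hours until day 7". The day-of-discharge row lists "COPD Assessment Test Spirometry CRP Serum sample saved" alongside capillary glucose and the EXACT score, with no renal test and no lactate. Between discharge and follow-up only EXACT is listed. Follow-up at day 28–35 includes lactate but no renal test.

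**Dose (9.5, 10.3).** The dose is fixed by study day and reaches 2000 mg/day on Day 4, whether the patient is in hospital or at home. The step before that is "Day 3: two capsules taken after breakfast time and one capsule after evening mealtime".

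**Entry (7.1, 6.2).** Criterion 4 is "Expected to remain in hospital for ≥48 hours", and patients are those "who are able to enter the study within 48 hours of admission".

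**Risk control (4.6.3, 9.10.2).** Against accumulation through renal failure, 4.6.3 says "we will monitor the renal function regularly while the participant is an inpatient" and undertakes to "stop or suspend the study treatment if the estimated GFR falls, or the serum creatinine rises, above pre-specified levels". Section 9.10.2 sets the limits: eGFR below 45 or creatinine above 130 µmol/L, and lactate of 3.0 mmol/L or more.

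**The concern.** The entry rules allow discharge by study Day 3, but the assessment table seems to be built around patients still in hospital on Day 4. A patient who leaves earlier passes between the Day 1 baseline and the Day 4 panel, and the discharge blood draw does not catch them.

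What is at stake is individual safety. The limits in 9.10.2 work only when something has been measured. For an early leaver, the one scheduled creatinine is the baseline value, and the only later scheduled lactate comes at the visit that ends treatment, too late to guide dosing.

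**Working it through.** The plan states no figure to reproduce here. The check has two parts: a reading of the schedule, and a rough estimate of how many patients it concerns.

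**1. Scheduled tests for a patient leaving on Day 3**

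| Time | Renal function | Lactate |
|---|---|---|
| Day 1 | yes | yes |
| Days 2–3 | no | no |
| Day of discharge | no | no |
| Discharge to follow-up | no | no |
| Day 28–35 | no | yes |

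A patient still in hospital on Day 4 is due a panel then, one 72-hour interval after Day 1, so there is no gap for that patient.

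**2. What a discharge sample could show**

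Dose taken by Day 3: 500 + 1000 + 1000 = 2500 mg before the evening dose, or 3000 mg after it. Section 4.3.1 puts steady state at 24–48 hours, so steady state at 2000 mg/day, which starts on Day 4, comes at about Day 5–6. A lactate on Day 3 or earlier is therefore only a check below the target dose. A creatinine is informative at any dose, because it tests the renal limit before about a month at full dose.

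**3. How many patients**

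Inputs from the protocol: length of stay with median 9 days (IQR 5–17), and median 8 days (IQR 4–16) in patients with diabetes, both in 6.4; target of 69 patients, of whom 69 × 2/3 = 46 on metformin at 2:1.

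Assumptions not in the protocol: stay is lognormal; entry is uniform over 0–2 days after admission; the clock time of entry is uniform over 09:00–17:00. Study days are taken as calendar days, because the dosing in 9.5 is tied to meals.

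- σ = ln(Q3/Q1)/(2 × 0.6745): ln(17/5)/1.349 = 0.907 and ln(16/4)/1.349 = 1.028; μ = ln(median).
- Stay after entry = total stay − entry lag.
- Discharge day = floor(stay after entry + clock hour/24) + 1; count those with day ≤ 3.

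Results from 6 million draws, first series / second series:

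| Reading of the 48-hour criterion | Share leaving by Day 3 | Of 69 |
|---|---|---|
| At least 48 h from entry | 3.6% / 4.4% | 2.5 / 3.0 |
| At least 48 h in total from admission | 10% / 13% | 7 / 9 |
| Expectation not always met | 13% / 18% | 9 / 13 |

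On the first reading, about 2 of the 46 on metformin are affected (46 × 0.036 = 1.7; 46 × 0.044 = 2.0). The chance of at least one is 1 − (1 − p)^46 = 82–88%.

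**The case against.** **The monitoring promise is kept.** The stated inpatient frequency is every 72 hours. A Day 3 leaver's last result is about two days old, so the second panel was not yet due. After day 7 the minimum is weekly, so a later leaver may go home on an older result. This stands. A reader might infer that 9.6 contradicts 4.6.3; it does not. What sets the early leaver apart is having no result after the first dose.

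**Most of the unmonitored exposure is not particular to this group.** A Day 3 leaver has 25–32 days to the next lactate and a planned 49–63 g from Day 4: (28 − 4) × 2000 + 1000 = 49,000 mg and (35 − 4) × 2000 + 1000 = 63,000 mg. A patient tested and discharged on Day 4 waits 24–31 days and takes nearly the same amount. These figures mainly reflect the deliberate choice in 4.6.3 to concentrate renal monitoring in the inpatient phase, so they should not be read as the size of this gap.

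**A lactate is scheduled at day 28–35.** This stands. It would be wrong to say that no lactate follows Day 1. Only creatinine is never scheduled again.

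**These are probably lower-risk patients.** Entry already excludes renal impairment, severe sepsis and metabolic acidosis, and 6.4 links a shorter stay with being less unwell. This is plausible and limits the gain. Routine clinical bloods, readmission review and the 24-hour line may also lead to suspension, but none guarantees a value. The provision for more frequent testing sits in the Day 4 row and does not reach these patients.

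**The discharge-row dose is not an error.** That row shows two capsules twice daily, which fits discharge on Day 4 or later. A reader might take this as a dosing contradiction, but 9.5 and 10.3 fix the dose by day and 9.6 is a summary, so the point is cosmetic.

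**Conclusion.** The point holds as a small gap in the safety schedule. A patient leaving by Day 3 has no scheduled creatinine after Day 1 and no scheduled lactate until treatment ends, so the 9.10.2 renal and lactate limits have no scheduled post-dose value to act on during treatment. No stated commitment is breached.

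The expected size is about 4%, or 2–3 of 69. This rests on the assumed lognormal stay and entry timing, calendar study days, and reading the 48 hours as running from entry, the most natural sense of remaining in hospital. It rises to about 13–18% if that expectation is not met. Neither length-of-stay series was selected for an expected 48-hour stay, so all these shares are indicative. The schedule reading itself is certain.

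**What to change.** In 9.6, add renal profile and plasma lactate to the day-of-discharge row unless already measured that day, and apply the existing 9.10.2 limits to the result. A lighter version would require this only for patients discharged before the Day 4 panel. No stopping rule changes. The 9.5 dose for that day could be noted in the same row for clarity.

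**Cost.** One extra tube and routine assays at the venepuncture already scheduled for CRP: at most 69 panels, or about 2–3 in the lighter version if the 48-hour expectation holds. A result may occasionally arrive after the patient has left and need a call-back.

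**What it does not do.** Early leavers still have no lactate at full dose before day 28–35. Changing that would mean outpatient testing, which is not proposed here.
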